On the first study day, we will place the Freestyle Libre Pro and continue monitoring for 2 weeks. Subjects will also complete baseline behavioral measures/dietary habit questionnaires. During this time, participants will be asked to take at least 3 photographs of their meals and send them to the researchers via text-messaging using MyCAP. Communication with participants via MyCAP will be done to confirm receipt of photos (e.g., "Good job with the photos yesterday, keep it up today!"), reminders if photos are missed (e.g., "It seems you sent fewer photos yesterday than your survey indicates meals you eat. If you missed a picture yesterday, remember to try and take photographs of all food today."), or tips to improve photos for image analysis (e.g., "Good job with the photos yesterday, but please try to adjust lighting/focus to properly capture all food.").

The subject will return after continuous wearing of the CGM monitor and sending of photos after the 2 weeks. At this second study day the CGM will be replaced and all data on the old CGM will be downloaded by the

researchers. The subject will then wear the new CGM monitor and continue to send pictures of all meals for 1 week before returning for their third visit.

At the third visit, a new CGM will be placed and the subject will be randomized into behavioral intervention.

1. One intervention will be based on counterfactual thinking, which will allow the subjects to think of an alternative reality that “might have been” based on the concurrency of their glucose readings and the meals they ate.
2. The control condition will use reflective writing. These subjects will be engaged in reflective writing intervention. They will look at your CGM readings throughout the first two weeks and compare them to the food eaten at those specific times. They will then be asked to reflect on the meals and how they feel about the changes in glucose levels based on the food choices made.

After this visit, they will then continue to wear the CGM monitor and take photos of their meals. They will return for their fourth visit in 2 weeks.

The fourth visit will consist of permanently removing the CGM monitor and conducting post-treatment interviews and behavioral measures/dietary habits with the subjects.

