Subjects will return for their fifth and sixth follow-up visit 2 months post intervention. At each of these visits their A1c will be measured through a blood collection of 4 mL by venipuncture. Delayed post-test interviews, and behavioral measures/dietary habits will also be conducted.

Description of the CBLI intervention

In the CBLI, participants will be shown healthy (low PPGR) and unhealthy (high PPGR) samples of their food photographs with the corresponding glucose responses (see Data Synchronization & Meal Selection & Figure 1b). For counterfactuals to be an effective self-regulatory tool, one needs information from a personal negative experience relevant to the current goal. Using healthy and unhealthy meal selections and their resulting CGM responses will make the causal relationship between food choices and glucose response more salient, and will increase the effectiveness of the counterfactual intervention, in which they generate ways they could have changed their food choices and subsequently improved the CGM response. Participants will be asked to compare the healthy and unhealthy meals and generate counterfactuals about how they could have altered the unhealthy meal (e.g., replace white bread with a tortilla) such that it would have improved the outcome (i.e., lower glucose responses). To increase the likelihood of participants generating accurate counterfactuals that could have improved their PPGR outcome, participants will be provided lists of effective eating strategies to aid their counterfactual generation. Afterwards, participants will evaluate each counterfactual thought and list at least one situation in the near future in which they could implement the eating behavior described in the counterfactual, and describe any barriers they imagine could reduce the likelihood of implementing the behavior. Our expectation is that the counterfactual thoughts generated during the intervention will lead to better food choices and increased motivation in the weeks that follow.

This session will be video recorded to ensure treatment fidelity and code participant responses.

Behavioral measures/dietary habit Questionnaires

General Health Intentions. Designed to collect ratings of intentions to engage in healthier food habits over the next six months.

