Motivation. The Regulation of Eating Behaviors Scale is designed to measure subject motivations for eating including to cope with negative affect, to be social, to comply with others' expectations, and to enhance pleasure.

Self-efficacy & Self-Regulation. Measured by the 5-item Eating Self-efficacy Scale and the Self-regulation of Eating Behavior Questionnaire.

Behavioral Intentions. Three items designed based on the Theory of Planned Behavior to measure intention to eat healthy using counterfactual strategies developed in Study Visit #3 (intervention group only).

Inclusion criteria

- Ability to walk, sit down and stand up independently
- Diagnosed with type 2 diabetes (T2D) and take glucose-lowering medication(s).
- Motivated to learn how to regulate blood glucose through non-medical intervention such as changes to eating behavior
- Subject is judged to be in satisfactory health based on medical history, physical examination
- Willingness and ability to comply with the protocol
 - Use your smartphone to upload pictures of meals through MyCap

Exclusion criteria

- Subject has planned elective surgery requiring 2 or more days of hospitalization during the entire study
- Allergy to adhesives
- Planned medical procedures that are documented to interfere with CGM readings, such as
 - Xylose absorption testing (oral sugar testing)
 - CT
 - MRI
 - X-ray
 - Diathermy treatment (high-frequency electric current to stimulate heat generation within body tissues)
- Established diagnosis of malignancy
- Presence of acute illness or metabolically unstable chronic illness
- Any other condition according to the PI, nurse, or study coordinator that was found during the screening visit, that would interfere with the study or safety of the patient
- Failure to give informed consent or Investigator's uncertainty about the willingness or ability of the subject to comply with the protocol requirements

When during the period from enrollment to completion of the study any condition is developed, whether causing the subject to not meet inclusion criteria or to meet exclusion criteria, the subject will be excluded from the study. Family history of type 2 diabetes will be used only for post-stratification of those who can report.

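### The exclusion rule does not stop at randomisation, so a participant who becomes ineligible after visit 3 loses the visit 4–6 outcomes still due

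*Protocol*

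**What the plan says.** The rule stands in the closing paragraph of the protocol's Exclusion criteria. It opens "When during the period from enrollment to completion of the study any condition is developed" and ends "whether causing the subject to not meet inclusion criteria or to meet exclusion criteria, the subject will be excluded from the study". The consequence is mandatory and applies to the study as a whole, not to a device or a session.

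Listed criteria that can arise at any time include "Presence of acute illness or metabolically unstable chronic illness" and "Established diagnosis of malignancy". The investigator-judgement criterion, by contrast, is limited to something "that was found during the screening visit".

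The Approach section sets the order of events:

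- **Visit 3:** "a new CGM will be placed and the subject will be randomized into behavioral intervention".
- **Visit 4, two weeks later:** "The fourth visit will consist of permanently removing the CGM monitor and conducting post-treatment interviews and behavioral measures/dietary habits with the subjects". No blood draw is listed.
- **Visits 5 and 6, two months after the intervention:** "At each of these visits their A1c will be measured through a blood collection of 4 mL by venipuncture". Interviews and questionnaires are repeated.

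Nothing in the protocol limits the rule to the time before randomisation or provides for data collection from a randomised participant who has been excluded.

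**The concern.** Eligibility criteria decide who enters a randomised comparison. Applied after allocation, they become a reason for losing outcome data. Here the rule covers the whole post-randomisation period and makes removal from the study the only consequence, even where the remaining assessments could still be done. For example, an adhesive allergy that appears after visit 3 is a listed criterion, but the later questionnaires, interviews and blood samples need no adhesive device.

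Two things are at stake. The first is precision, in a trial of at most 40. The second is comparability of the arms, if the chance of exclusion depends on the arm. The protocol does not say whether a condition means a medical condition or any listed criterion. The inclusion criteria contain motivation and willingness to comply. Motivation is also one of the five measures in the Specific Aim, and the description of the counterfactual intervention expects it to rise in that arm. On the wider reading, exclusion could therefore be a consequence of the assigned arm.

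**Working it through.** The protocol gives no power calculation, allocation ratio or exclusion rate, so there is no stated figure to reproduce. The check sets the rule against the visit schedule and then illustrates the size under stated assumptions.

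**1. What is lost, by time of exclusion**

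| Exclusion falls | Outcomes no longer collected |
|---|---|
| Between visits 3 and 4 | Rest of the post-randomisation CGM record, visit 4 questionnaires and interview, everything at visits 5 and 6 |
| Between visits 4 and 5 | Delayed questionnaires and interviews, A1c at visits 5 and 6 |
| Between visits 5 and 6 | Visit 6 only |

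On the visit-by-visit schedule, anyone excluded before visit 5 has no A1c after the intervention. The study design paragraph instead describes two samples in all, at screening and on the last study day, so the A1c schedule is itself not fully settled. A1c is not among the five aim measures.

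**2. Precision**

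Assumptions: all 40 randomised, 20 per arm, two-sample t-test, two-sided 5% level, 80% power. The detectable standardised difference d solves

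P(|T| > t₀.₉₇₅) = 0.80, where T is noncentral t with n₁ + n₂ − 2 degrees of freedom and noncentrality d / √(1/n₁ + 1/n₂).

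| Analysed | Per arm | Detectable difference (SD) |
|---|---|---|
| 40 | 20 + 20 | 0.909 |
| 39 | 20 + 19 | 0.922 |
| 38 | 19 + 19 | 0.934 |
| 36 | 18 + 18 | 0.961 |

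**3. Bias, wider reading only (illustration)**

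Let the outcome Y and the excluding trait T be standard normal with correlation r. The intervention shifts Y by 0.50 SD and T by s. Participants stay in if T > c, where c = −1.645 removes 5% of controls (1 of 20). With λ(x) = φ(x) / (1 − Φ(x)), the observed effect is

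0.50 + r × [λ(c − s) − λ(c)], with λ(−1.645) = 0.1086.

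| r | Shift in T (s) | λ(c − s) | Intervention arm excluded | Observed effect (SD) |
|---|---|---|---|---|
| 0.3 | 0.15 (= 0.50r) | 0.0827 | 3.6% | 0.492 |
| 0.5 | 0.25 (= 0.50r) | 0.0682 | 2.9% | 0.480 |
| 0.3 | 0.50 | 0.0406 | 1.6% | 0.480 |
| 0.5 | 0.50 | 0.0406 | 1.6% | 0.466 |

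Example, last row: 0.50 + 0.5 × (0.0406 − 0.1086) = 0.466. The bias runs from 0.008 to 0.034 SD. A simulation with 3 million per arm gave 0.493, 0.480, 0.480 and 0.467, in agreement.

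In the mirror case, with 5% of the intervention arm and fewer controls removed, the observed effects are 0.508, 0.520, 0.520 and 0.534 SD. The direction therefore depends on which arm loses more people.

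**The case against.** The strongest objection is that the effect is small and the more serious route is unlikely. Several features favour a narrow medical reading: a condition is something that develops, one criterion is tied expressly to screening, and missed photographs lead to reminders rather than removal. On that reading no clear route to arm-dependent exclusion is shown, and four exclusions move the detectable effect only from 0.91 to 0.96 SD. Even the largest illustrated bias, 0.034 SD, is about one tenth of the standard error of the difference (√(2/20) = 0.32 SD). The CGM measure and the first post-treatment questionnaires are complete two weeks after randomisation, so exposure for those is short. The protocol also never says outright that follow-up stops or that data already collected are discarded, and analysis sets may be defined in a plan not shown.

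The points on size and on the narrow reading stand, and they limit the severity. They do not remove the problem. That follow-up ends is an inference, but it is the plain meaning of exclusion from the study, and the protocol offers nothing else. An analysis set can use only data that were collected, so an analysis plan could not repair this.

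**Conclusion.** The concern holds. The protocol fixes a rule that, followed as written, stops collection of outcomes from randomised participants for reasons of eligibility, with no line drawn at visit 3. It should be fixed, but it does not by itself undermine the trial.

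On the medical reading the expected cost is a small loss of precision: 0.91 to 0.96 SD detectable for 40 down to 36 analysed, assuming 20 per arm and exclusion unrelated to arm and outcome. On the wider reading the comparison could be biased in either direction. The illustrated 0.008 to 0.034 SD depends wholly on the assumed 5% exclusion in one arm, true effect of 0.50 SD and correlation of 0.3 to 0.5. The actual amount is unknown because the protocol gives no rates. Confidence is medium, mainly because the meaning of a condition is left open.

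**What to change.** Amend the closing paragraph of the Exclusion criteria in three respects:

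- Apply eligibility-based exclusion only up to randomisation at visit 3.
- After randomisation, separate stopping the intervention or the device from ending follow-up, and keep collecting visit 4–6 outcomes where consent allows, so that participants can be compared by assigned arm.
- State whether a condition means a medical condition or any listed criterion, including motivation and compliance.

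Which events stop study procedures for safety remains for the protocol authors to decide.

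The cost is one or two sentences and continued follow-up of probably a few participants. The downside is slightly more follow-up work and some added noise from participants who are ill when assessed.
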